4.2 Study definitions of infection and illness

Illness/infection type	Definition
Viral shedding	A positive molecular test for influenza
MMID (Mild to moderate influenza induced disease)	
Detectable viral shedding plus at least one of the following symptoms or signs or tests determined by the investigator to be related to influenza:
 
• Arthralgia• Chills• Conjunctivitis• Coryza• Diarrhoea• Dry Cough• Dyspnea/Shortness of Breath• Fatigue/Tiredness• Fever ($>38.0^{\circ}\text{C}$)• Headache• Myalgia• Nausea• Oxygen Saturation Decrease by $\geq 3\%$ from baseline• Productive Cough• Rhinorrhea• Sore Throat• Sweats

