8.4 Alcohol, caffeine and xanthine-containing food and beverages

Subjects should abstain from alcohol, caffeine and xanthine-containing food and beverages (e.g., coffee, tea, energy drinks, cola, chocolate) between 24 hours prior to vaccine and dosing as well as prior to admission to quarantine. They will continue to abstain until after discharge from quarantine unit. Decaffeinated drinks will be provided during the quarantine period.

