13.2 Efficacy assessments

Assessments to determine the efficacy of the IMP will be performed at the times detailed in T&E. Unless otherwise indicated, the value obtained at screening will be used as the baseline for efficacy assessments.

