13.2.2 FLU-PRO Symptom Severity Assessment Tool and Physician assessment of Influenza Symptoms

Subjects will report and assess any Challenge Virus related signs and symptoms and assess their associated severity using the FLU-PRO Symptom Severity Assessment. The physician assessment will be performed daily to determine the presence or absence of influenza symptoms. The following mild (Grade 1) to moderate (Grade 2) signs or symptoms are induced by or associated with influenza, and any combination of these is expected to occur with virus challenge. These symptoms will not be reported as adverse events unless they are associated with administration of FLU-v and deemed possibly, probably, or definitely related to FLU-v by the PI. If deemed related to influenza by the PI they will be recorded as Adverse Events of influenza infection per protocol, only if deemed a risk to the participants' rights or wellbeing or as deemed appropriate by the Principal Investigator. The study team on a daily basis will check these events.

In the event of missing FLU-PRO Symptom Severity Assessment Tool data, the physician will review the data in retrospect, and complete the information as accurately as possible by asking the subject about any symptoms during the missing day. However, no protocol deviation will be recorded for missing FLU-PRO Symptom Severity Assessment Tool data.

- Arthralgia
- Chills
- Conjunctivitis
- Coryza
- Diarrhea
- Dry Cough
- Dyspnea/Shortness of Breath
- Fatigue/Tiredness
- Fever ($>38.0^{\circ}\text{C}$)
- Headache
- Myalgia
- Nausea
- Oxygen Saturation Decrease by $\geq 3\%$ from baseline
- Productive Cough
- Rhinorrhea
- Sore Throat
- Sweats

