16.5 Primary analysis

The primary analysis will be performed to evaluate the MMID rate in each of the three groups. This will be based on the physician assessment (presence or absence of symptoms) and the influenza PCR performed on nasal swab (demonstrating viral shedding). MMID rates in the 2

FLU-v groups and placebo group will be compared using a Fishers exact test. 95% confidence intervals around the difference in rates between the FLU-v groups will be presented.

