5.1 Primary Objective

To determine the effect of FLU-v in reducing the incidence of Mild to Moderate Influenza Induced Disease (MMID) defined as detectable viral shedding plus at least one symptom of influenza from Day 1 post-inoculation until Day 7. Day 1 post-inoculation evaluations were completed in the evening of Day 1, more than 24 hours post-inoculation.

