5.2 Primary Endpoint: Incidence of MMID

MMID is defined as positive if a participant has both detectable shedding, as evaluated by RT-qPCR (reverse transcriptase quantitative polymerase chain reaction), and at least one symptom,

as observed on the Physician Assessment of Influenza Symptoms (PAI), at any time during subject quarantine, starting from the evening of Day 1 post-inoculation through the expected end of the quarantine period, Day 7, Discharge. The analysis of this endpoint will be performed by comparing the MMID rates in each of the FLU-v groups to the placebo group. Comparisons will be performed using one-sided Fisher's exact test, and the proportion of subjects with MMID and corresponding p-value will be presented. If a subject has no nasal swab data on two consecutive days, and the available recorded data shows no shedding, the MMID for that subject will be considered as missing. Similarly, if symptom data is not recorded on two consecutive days, and the available recorded data shows no symptoms, the MMID will be considered as missing for that subject. However, if a subject is positive for viral shedding and experiences at least one symptom with the available recorded data, that subject will be included in the MMID analysis. The primary analysis will incorporate missing data as described in section 5.7. The statistical summary data will be presented as tables and figures as described in sections 8-9 of this document.

5.3 Secondary Objectives:

To determine the overall effect of FLU-v on influenza disease based on disease severity measures (presence or absence of symptoms or shedding, symptom severity, symptom and shedding duration, total symptoms and shedding, and peak symptom and shedding). Viral shedding was evaluated by RT-qPCR and symptoms were evaluated by PAI, from the evening of Day 1 post-inoculation (more than 24 hours after inoculation) through the expected end of the quarantine period (Day 7, Discharge).

5.4 Secondary Endpoints:

- Overview of symptoms (PAI) and of viral shedding (RT-qPCR) from the evening of Day 1 post-inoculation (more than 24 hours after inoculation) through Day 7.

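### The documents define the primary endpoint MMID in two ways, by influenza-related symptom or by mere presence on the PAI, and neither sets symptoms against the pre-challenge PAI

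*SAP*

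**What the plan says.** Four sections bear on what counts as a symptom.

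- Protocol 4.2 defines MMID as "Detectable viral shedding plus at least one of the following symptoms or signs or tests determined by the investigator to be related to influenza", followed by 17 items.
- Protocol 16.5 specifies the primary analysis: "This will be based on the physician assessment (presence or absence of symptoms) and the influenza PCR performed on nasal swab". It does not mention relatedness.
- SAP 5.1 keeps the phrase in the objective: "defined as detectable viral shedding plus at least one symptom of influenza from Day 1 post-inoculation until Day 7".
- SAP 5.2, the operational rule, needs shedding by RT-qPCR and at least one symptom "as observed on the Physician Assessment of Influenza Symptoms (PAI), at any time during subject quarantine", counted from the evening of Day 1 to Day 7. It has no relatedness condition and no pre-challenge comparison, and does not require symptom and shedding on the same day.

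SAP section 6 declares no change from the protocol-specified analyses other than the post-hoc ones, plus a note on sample size.

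The Time & Events schedule (protocol Table 9-2) places the PAI once at admission (Day -2 or Day -1) and then daily from Day 0 to Day 7. A pre-challenge record therefore exists, but no rule uses it. The only MMID item defined against a baseline is oxygen saturation. For that item, protocol 13.1 takes the baseline before IMP, whereas protocol 13.2 says: "Unless otherwise indicated, the value obtained at screening will be used as the baseline for efficacy assessments".

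**The concern.** A statistician programming MMID cannot tell which definition governs. Under protocol 4.2, a shedder whose only entry is a headache judged unrelated to influenza is not a case. Under SAP 5.2 that subject is a case. The same applies to an item present at admission that persists into Day 1.

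Many of the 17 items are non-specific: headache, tiredness, nausea, rhinorrhea, sore throat. The protocol's own summaries show that such items occur without influenza, or are attributed to something else. In FLU-v-001, which had no challenge, subjects given FLU-v reported headache (11 events), fatigue (9), myalgia (7) and nausea (4). In FLU-v-002, rhinorrhoea was judged IMP-related in 4 of 16 FLU-v and 3 of 16 placebo subjects. These figures do not give a seven-day quarantine rate, but they show that the background is not zero.

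False events can fall only on shedders without influenza symptoms. FLU-v does not raise neutralising antibodies (protocol 5.2), so turning illness into silent shedding is a plausible benefit, and the SAP has a secondary endpoint for asymptomatic infected subjects. If that is how the vaccine works, the false events fall mainly in the FLU-v arms and shrink the primary contrast.

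**Working it through.** **Stated figure.** Protocol 16.2 gives 41 per arm, MMID 0.70 v 0.40, one-sided alpha 0.05 and 80% power. Exact enumeration of the one-sided Fisher test gives 81.3% at n = 41, and 79.8% at the SAP's n = 40. All nine rows of the protocol's power table reproduce within 2 points. The continuity-corrected formula gives n = 40 and n = 37, matching SAP Table 1.

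**Inputs not in the documents (assumed).** b is the chance that a shedder without influenza-caused symptoms has at least one other PAI item in the scoring window; the range used is 0.1 to 0.5. s is the shedding rate in each arm, with placebo at 0.80.

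**Formula.** With m the influenza-related MMID rate in an arm:

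observed MMID = m + b × (s − m)

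observed difference = 0.30 × (1 − b) + b × (s_placebo − s_vaccine)

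The difference therefore shrinks whenever FLU-v lowers shedding by less than 0.30, and does not shrink otherwise.

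**Results** (exact one-sided Fisher power, n = 41):

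| Shedding, placebo v vaccine | b | Observed MMID | Difference | Power |
|---|---|---|---|---|
| any | 0 | 0.70 v 0.40 | 0.30 | 0.813 |
| 0.80 v 0.60 | 0.1 | 0.71 v 0.42 | 0.29 | 0.788 |
| 0.80 v 0.60 | 0.2 | 0.72 v 0.44 | 0.28 | 0.762 |
| 0.80 v 0.60 | 0.5 | 0.75 v 0.50 | 0.25 | 0.680 |
| 0.80 v 0.80 | 0.1 | 0.71 v 0.44 | 0.27 | 0.730 |
| 0.80 v 0.80 | 0.2 | 0.72 v 0.48 | 0.24 | 0.633 |
| 0.80 v 0.80 | 0.5 | 0.75 v 0.60 | 0.15 | 0.335 |
| 0.80 v 0.457 | 0.1 | 0.71 v 0.406 | 0.304 | 0.825 |
| 0.80 v 0.457 | 0.2 | 0.72 v 0.411 | 0.309 | 0.836 |
| 0.80 v 0.457 | 0.5 | 0.75 v 0.429 | 0.321 | 0.870 |

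Example, second block at b = 0.2: placebo 0.70 + 0.2 × (0.80 − 0.70) = 0.72; vaccine 0.40 + 0.2 × (0.80 − 0.40) = 0.48.

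The last block is the case in which the vaccine works only by preventing shedding, with the same chance of symptoms in every shedder: 0.80 × 0.40 / 0.70 = 0.457. The risk ratio stays at 0.571 and power rises slightly.

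**The case against.** **The PAI may already carry the judgement.** It is a physician's assessment of influenza symptoms: "The physician assessment will be performed daily to determine the presence or absence of influenza symptoms". A tick could be the relatedness decision that protocol 4.2 asks for, and SAP 5.1 still speaks of a symptom of influenza. This stands in part. The form is not in the documents, so it is not shown that every unrelated symptom would be counted. But no text says that an entry implies attribution, and protocol 13.2.2 treats presence and attribution of the listed symptoms as separate steps. The PAI is also scheduled before challenge, so an entry cannot by itself mean challenge-induced illness.

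**The SAP changed nothing.** A reader might infer that the SAP removed a protocol condition, or a baseline rule. The documents do not support that. Protocol 16.5 already reduces the primary analysis to presence or absence, and SAP 5.2 follows it. Neither document ever required a symptom baseline, apart from the oxygen-saturation item. The conflict starts inside the protocol.

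**Safeguards exist.** Scoring starts more than 24 hours after inoculation. There is a respiratory virus screen at admission, a possible post-hoc analysis without co-infected subjects, and a Modified MMID needing two symptoms. Caffeine stops 24 hours before admission, so early withdrawal symptoms may have passed. These measures reduce the background, but none applies relatedness or a baseline to the primary endpoint.

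**The dilution is conditional.** This stands. The lowest power needs both b = 0.5 and no effect on shedding, although protocol 5.2.2 reports lower viral titres in vaccinated animals. The planned 0.70 rests on past experience (SAP section 4) and may already include background symptoms.

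**Oxygen saturation.** A reader might infer that a screening baseline yields more chance falls than an admission baseline. The documents give no within-subject variability or drift to support that. Without drift between visits, the two baselines give the same rate of chance falls. What stands is only that two different baselines are stated.

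**Conclusion.** The primary endpoint has two definitions, and the SAP follows one without noting the other. This is a matter of text and needs no assumption. The rule as written also ignores a pre-challenge symptom record that the trial collects.

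The size of the effect is uncertain. For b of 0.1 to 0.5, the difference of 0.30 falls to 0.29-0.25 with power 79%-68% (shedding 0.80 v 0.60), or to 0.27-0.15 with power 73%-34% (shedding 0.80 in both arms), against 81% for the stated design. With an effect only through shedding, power is 83%-87%. All of this rests on assumed background and shedding rates, and on 0.70 v 0.40 being free of background symptoms.

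Two stronger conclusions do not follow. Dilution is not certain, because it depends on how the vaccine acts. Nor does the rule favour FLU-v: assessors are blinded, and where background symptoms do dilute, they work against finding an effect. The point should be fixed; it is not fatal to the trial.

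**What to change.** Before unblinding:

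1. Reconcile protocol 4.2, protocol 16.5 and SAP 5.2, and record the outcome in SAP section 6.
2. State in SAP 5.2 whether a PAI entry carries the investigator's relatedness judgement. If relatedness is recorded by item, apply it. If not, say so and do not reconstruct it afterwards; the SAP already describes evaluations in the past tense.
3. Do not count a PAI item that was present at the last pre-inoculation PAI (Day -2/-1, or Day 0 if done before inoculation). At the least, pre-specify this new-onset MMID as a named sensitivity analysis beside the any-symptom version. The rule must be new onset only, since a presence/absence record cannot show worsening.
4. State one baseline for the oxygen-saturation item, because protocol 13.1 and 13.2 differ.

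Cost: wording, and one further derivation from data already scheduled. No new assessment is needed. Two drawbacks should be accepted openly: the placebo MMID rate may fall slightly, and a true influenza symptom may be missed in a subject who already had that item before inoculation.

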 - If a subject has no nasal swab data on two consecutive days, and the available recorded data shows no shedding, the endpoint will be considered as missing. Similarly, if symptom data is not recorded on two consecutive days, and the available recorded data shows no symptoms, the endpoint will be considered as missing for that subject. However, if a subject is positive for viral shedding with the available recorded data, that subject will be included in the analysis. Similarly, if the subject shows at least one symptom within the recorded data, that subject will be included in the analysis.

- Modified MMID
 - Incidence of at least two symptoms (on PAI) and viral shedding (RT-qPCR) at any time during the quarantine from evening of Day 1 post-inoculation through Day 7. If a subject has no nasal swab data on two consecutive days, and the available recorded data shows no shedding, the Modified MMID will be considered as missing. Similarly, if symptom data is not recorded on two consecutive days and the available recorded data shows no symptoms this endpoint will be considered as missing for that subject. However, if a subject is positive for viral shedding and experiences at least two symptoms with the available recorded data, that subject will be included in the modified MMID analysis.
- Viral shedding duration (days)
 - Measured from the first day with a positive test on RT-qPCR, starting from evening of Day 1 post-inoculation until the last day with a positive test during the expected quarantine period (up to Day 7). Intervening negative or missing test days will be included in the duration. If no positive test occurs, duration is counted as zero.
- Viral shedding quantitation (RT-qPCR)

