5.7.1 Primary endpoint

- Primary analysis: impute the placebo group's proportion of events for the missing data in each group.
- Sensitivity analysis: ignore missing data.
- Sensitivity analysis: for placebo group impute observed proportion from vaccine group and for vaccine group impute observed proportion from placebo group.

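### SAP 5.2 sets MMID to missing for some subjects whose complete, negative other component already makes them non-cases, and SAP 5.7.1 then imputes the placebo event rate for them

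*SAP*

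**What the plan says.** SAP 5.2 makes MMID an and-composite: "MMID is defined as positive if a participant has both detectable shedding" on RT-qPCR and at least one symptom on the physician assessment (PAI), between the evening of Day 1 and Day 7.

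Two rules then set MMID to missing, each looking at one component alone. For swabs, after a two-day gap, if "the available recorded data shows no shedding, the MMID for that subject will be considered as missing". For symptoms, "if symptom data is not recorded on two consecutive days, and the available recorded data shows no symptoms, the MMID will be considered as missing". Neither refers to the state of the other component. The one exception stated is for recorded cases: "if a subject is positive for viral shedding and experiences at least one symptom with the available recorded data", the subject stays in.

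SAP 5.7.1 handles the missing values: "Primary analysis: impute the placebo group's proportion of events for the missing data in each group". Its two sensitivity analyses drop the missing subjects, or swap the observed proportions between placebo and vaccine groups.

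SAP 5.4 carries the same construction into Modified MMID ("If a subject has no nasal swab data on two consecutive days, and the available recorded data shows no shedding, the Modified MMID" is treated as missing). There SAP 5.7.3 drops missing subjects in the primary analysis. The blinded data review in SAP section 5 decides membership of the per-protocol set; it is given no role in settling MMID status.

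**The concern.** A subject with a complete, symptom-free PAI record cannot be an MMID case, whatever the unseen swabs would have shown. The same is true of a subject whose swab record is complete and negative but whose PAI has a two-day gap. The component-wise rule suits endpoints that report shedding and symptoms separately. It does not suit a composite that requires both. A known zero is turned into an unknown and then given roughly 0.7 of an event.

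What is at stake is the primary comparison. If FLU-v works, it should leave more subjects with neither shedding nor symptoms. If gaps are equally frequent among such subjects, FLU-v is likely to contain more misclassified zeros, and the estimated difference shrinks.

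**Working it through.** **Step 1: which records are affected.** Gap means two consecutive days unrecorded; complete means no such gap, which is the SAP's own standard.

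| Swab record | PAI record | SAP 5.2 | What the definition implies |
|---|---|---|---|
| Gap, no shedding seen | Complete, no symptom | Missing | **No** |
| Complete, negative | Gap, no symptom seen | Missing | **No** |
| Gap, no shedding seen | Symptom seen | Missing | Undetermined |
| Shedding seen | Gap, no symptom seen | Missing | Undetermined |
| Gap, no shedding seen | Gap, no symptom seen | Missing | Undetermined |
| Gap, shedding seen | Complete, no symptom | Not triggered, stays No | No |
| Complete, negative | Gap, symptom seen | Not triggered, stays No | No |
| Shedding seen | Symptom seen | Case | Case |

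Only the first two rows are wrong.

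**Step 2: does another analysis count these subjects as zeros?** No. The primary analysis imputes the placebo proportion. One sensitivity analysis removes them from the denominator. The other gives FLU-v subjects the placebo proportion again and placebo subjects the vaccine proportion.

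**Step 3: reproduce the plan's power.** Inputs: MMID 0.70 v 0.40, one-sided alpha 0.05 (protocol 16.2, SAP section 4), one-sided Fisher test (SAP 5.2). Exact enumeration gives 0.813 with 41 per arm (protocol states 80%) and 0.798 with 40 per arm (SAP states 80%). All nine rows of the protocol's power table reproduce within 0.02.

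**Step 4: shift per affected subject.** 0.70/41 = 0.0171, or 1.7 percentage points in place of 0.

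**Step 5: power with assumed numbers affected.** FLU-v rate = 0.40 + 0.70 × m(F)/41; placebo rate = 0.70 + 0.70 × m(P)/41. Exact one-sided Fisher power, 41 v 41:

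| Affected, FLU-v v placebo | Placebo | FLU-v | Difference | Power |
|---|---|---|---|---|
| 0 v 0 | 0.700 | 0.400 | 0.300 | 0.81 |
| 1 v 0 | 0.700 | 0.417 | 0.283 | 0.77 |
| 2 v 1 | 0.717 | 0.434 | 0.283 | 0.77 |
| 4 v 2 | 0.734 | 0.468 | 0.266 | 0.72 |
| 1 v 1 | 0.717 | 0.417 | 0.300 | about 0.81 |
| 2 v 2 | 0.734 | 0.434 | 0.300 | about 0.82 |

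As a cross-check, suppose 10% of non-cases in each arm are affected: 0.10 × 0.30 × 41 = 1.2 in placebo and 0.10 × 0.60 × 41 = 2.5 in FLU-v. The imputed proportion is then 0.70/(1 − 0.30 × 0.10) = 0.722, because only non-cases leave the placebo denominator. Simulated power is 0.76 to 0.77. The SAP does not say how a proportion enters a Fisher table; a random draw and a rounded count gave similar results.

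**Step 6: one data set.** With 29/41 v 20/41 cases, one-sided p = 0.035. If one affected FLU-v subject is imputed as an event, 29/41 v 21/41 gives p = 0.056. If that subject is dropped, 29/41 v 20/40 gives p = 0.046.

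**Step 7: no vaccine effect.** With 0.70 in both arms and equal gap rates, the simulated rejection rate is about 0.03 without the rule, and 0.025 to 0.031 with 5% to 30% of non-cases affected.

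**The case against.** The best defence is that this will rarely happen and errs on the safe side. Protocol Table 9-2 has swabs twice daily and the physician assessment daily in an inpatient unit, so a swab trigger normally needs four missed samples while every PAI is still done. The likeliest cause of a gap, early departure, stops both records, and such a subject really is undetermined. SAP 5.7 calls missing data unlikely. Equal numbers affected cost no power.

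All of that stands, and it limits the size. It does not justify the rule: conservative imputation is reasonable when status is unknown, whereas here the recorded data settle it.

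Four stronger readings are tempting, and the documents do not support them:

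- *All non-cases are exposed, so FLU-v is hit twice as hard (60% v 30%).* Only subjects with neither shedding nor symptoms recorded are exposed. Asymptomatic shedders with a symptom gap, and symptomatic non-shedders with a swab gap, are correctly missing. The plan gives no split of non-cases, so 2:1 is an assumption.
- *Dropping missing subjects keeps those with gaps only when they are positive.* Rows six and seven of the table above are negatives with gaps that stay in as No.
- *FLU-v is always inflated most.* The error per affected subject is the same in every arm. The ordering needs a working vaccine and similar gap rates.
- *The rule raises false positives.* With balanced gaps it does not.

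**Conclusion.** The point holds as a defect in the derivation of the primary endpoint. SAP 5.2 classes as missing some subjects who are non-cases by its own definition and completeness standard, and no planned analysis restores them. The size per subject is fixed at about 1.7 points at planning rates; the number of such subjects is not given and is expected to be low. Under an assumed 2:1 split, power falls from 0.81 to 0.77 (2 v 1) or 0.72 (4 v 2). With equal counts nothing is lost. If the vaccine works and gaps are balanced, the likely direction is toward no effect. Because one subject can move a borderline p-value across 0.05, it should be fixed, but the evidence does not make it critical.

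**What to change.** In SAP 5.2, before unblinding and documented as a SAP change, replace the two missing-data sentences with:

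*MMID = No if either component meets the completeness standard (no two consecutive days unrecorded) and is negative throughout, whatever the gaps in the other component. MMID = missing only if no case is recorded and neither component alone rules MMID out.*

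In SAP 5.4 apply the same logic to Modified MMID: a complete PAI record with at most one symptom, or a complete swab record with no shedding, gives No. Leave the imputation in SAP 5.7.1 as it is for subjects who remain undetermined. Report by arm how many subjects the change reclassifies.

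The text and programming are small. The real cost is procedural. The SAP already gives counts of inoculated subjects (section 5.8) and the size of the per-protocol difference (section 8), and the change is likely to favour FLU-v, so the reason must be recorded while the study is still blind. Subjects with single-day gaps are treated as complete, as the SAP already does, so a few coded No will not be strictly certain.

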16.2 Sample size

The primary objective of this study is to examine whether there is a difference in the MMID rates post inoculation between either of the 2 FLU-v arms and placebo. A sample size of 41 subjects per arm (total 123) will provide 80% power to detect a difference in MMID rates of .70 versus .40 using a one sided 0.05 significance level. The table below shows the power that the study would have with 41 patients per arm for other MMID rates. The sample size calculations do not adjust for multiple comparisons.

Table 1. Power with 41 subjects per arm with various MMID probabilities

Probability of MMID in placebo	Probability of MMID in Vaccinated arms	Power
.70	.40	.80
.70	.44	.70
.70	.47	.60
.60	.30	.80
.60	.34	.70
.60	.37	.59
.50	.21	.81
.50	.25	.68
.50	.28	.56

In this study the main comparisons are for each of the FLU-v dose groups to placebo. The study will also compare the FLU-v dosing arms but the study will not have adequate power to detect a significant difference in MMID rates at the predicted treatment rates. This study does not control for multiple comparisons since we are trying to maintain a small sample size but yet have high power to detect the pre-defined primary objective of efficacy versus placebo when FLU-v is truly beneficial. All comparisons will be made at the one sided 0.05 significance level.

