A randomized, double-blind, placebo-controlled efficacy and safety trial of FLU-v administered as 2 vaccinations or 1 vaccination vs placebo prior to intranasal challenge with the Influenza A 2009 H1N1 human virus.

In this study, the main efficacy comparisons are for each of the FLU-v groups to placebo. The study will not compare the two FLU-v dosing arms as the study may not have enough power to detect a significant difference in the primary efficacy endpoint of mild to moderate influenza induced disease (MMID) rates between the FLU-v groups.

2 Current Approved Study Protocol

The current approved study protocol is version 3.0 dated 18APR2017.

3 Study Hypothesis

The hypothesis is that vaccination with one dose or two doses of FLU-v + adjuvant will significantly reduce MMID when compared to individuals vaccinated with placebo.

4 Sample Size Justification and Analysis Plan

Sample size was calculated for 3 groups, a placebo group and 2 Investigational Medicinal Product (IMP) (i.e. one dose and two doses of FLU-v) groups. Each FLU-v arm will be compared to the placebo arm. Groups are randomized 1:1:1. All comparisons are at the 0.05 one-sided alpha level, and any p-value less than 0.05 would be considered as significant. This may increase the type-I error rate of potentially moving forward with an inactive treatment, but is appropriate for an early phase II trial of this type. Sample sizes assuming two different placebo MMID rates and for 80% power are given in Table 1 below.

Table 1.

Probability (rate) of MMID		Sample size per arm	Total sample size	Power	One-sided alpha
Placebo	Vaccine				
0.7	0.4	40	120	80%	0.05
0.8	0.5	37	111	80%	0.05

Table 1 shows that a sample size of 120 (40 per group) provides good power (80%) for a placebo MMID rate of 0.7 and an absolute reduction of 30%. The difference is clinically meaningful and the assumptions of a placebo MMID rate of 0.70 is reasonable and based on past experience.¹

5 Analysis Plan and Reports

The primary analysis population will be the Intent to Treat (ITT) population and will be used for the analysis of all primary and secondary endpoints. The ITT will include those participants who received both vaccination and challenge with an influenza virus.

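### The MMID missing-data rule sets some settled non-cases to missing, imputes the placebo rate for them in the primary analysis, and does not say how a proportion becomes an integer count for Fisher's exact test

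*SAP*

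**What the plan says.** SAP 5.2 defines a case as a subject with both RT-qPCR shedding and at least one symptom on the physician assessment, between the evening of Day 1 and Day 7. It then gives two separate missing-data rules. A two-day gap in swabs with no recorded shedding makes MMID missing. For symptoms, if "symptom data is not recorded on two consecutive days, and the available recorded data shows no symptoms, the MMID will be considered as missing". Neither rule looks at the other component. The only exception keeps subjects who are already positive on both.

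For subjects set to missing, the primary analysis in SAP 5.7.1 imputes the placebo group's "proportion of events for the missing data in each group", so the placebo arm is filled at its own rate too. The two sensitivity analyses ignore missing data or exchange the arms' proportions. For the test, SAP 5.2 says "Comparisons will be performed using one-sided Fisher's exact test". Nothing is said about rounding, random draws or multiple imputation. SAP 5.7 describes missing data as unlikely and gives no rate.

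Two rules for secondary endpoints in SAP 5.4 are related. Modified MMID needs at least two symptoms, but its symptom-gap rule applies only where "the available recorded data shows no symptoms this endpoint will be considered as missing". For shedding duration, "If no positive test occurs, duration is counted as zero".

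**The concern.** An endpoint that needs two conditions is settled as negative once either condition is known to be absent. A subject whose swabs are all negative with no two-day gap is a non-case whatever happened to the symptom record, and the reverse also holds. The SAP discards that knowledge and replaces a value of 0 with roughly 0.7 in the primary analysis. Both sensitivity analyses use the same missing flag: one drops these subjects and the other refills them. No planned analysis of the primary endpoint counts them as non-cases.

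The second problem is the form of the imputed value. Fisher's exact test needs integer counts, and a proportion applied to one or two subjects does not supply them. Different reasonable conventions can give different conclusions from the same data. Protocol 16 has the unblinded statistician perform the analysis, so the convention should be in writing beforehand.

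**Working it through.** **Inputs.** Protocol 16.2: "A sample size of 41 subjects per arm (total 123) will provide 80% power" for 0.70 v 0.40, one-sided 0.05. SAP 4 gives 40 per arm for the same target and says "All comparisons are at the 0.05 one-sided alpha level". Test and imputation are from SAP 5.2 and 5.7.1. *Assumption:* a share q of true non-cases in each arm is settled but flagged missing; q = 2, 5 and 10%, with 20% as an outer case. The documents give no figure.

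**1. The plan's own figure.** Exact enumeration of one-sided Fisher power at 0.70 v 0.40 gives 0.813 with 41 per arm and 0.798 with 40. The stated 80% is reproduced.

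**2. Who is affected.** The subject has a two-day gap in one component with nothing recorded in it, and the other component is negative with no two-day gap. If the other component is positive, or has a two-day gap with nothing recorded in it, status is open and missing is the right code.

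**3. Size of the error.** Let xp and xv be true cases, mp and mv the flagged settled non-cases (placebo, FLU-v), n the arm size and r = xp/(n − mp). Taken literally, the imputed counts are xp + mp·r and xv + mv·r. The rate difference is therefore (xp − xv)/n + (mp − mv)·r/n, and the error is **(mp − mv)·r/n**. One flagged FLU-v non-case at r = 0.7 shifts the difference by 0.7/41 = 1.7 points.

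**4. At the design rates.** Expected non-cases are 0.60 × 41 = 24.6 on FLU-v and 0.30 × 41 = 12.3 on placebo, so equal gap rates flag about twice as many on FLU-v. At q = 10%: r = 0.70/(1 − 0.10 × 0.30) = 0.722; placebo becomes 0.70 + 0.03 × 0.722 = 0.722; FLU-v becomes 0.40 + 0.06 × 0.722 = 0.443; the difference is 0.278 instead of 0.300. Power below is from 200,000 simulated trials under three rounding conventions.

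| q | mean flagged, placebo / FLU-v | difference | power, nearest | power, rounded against FLU-v | power, rounded for FLU-v |
|---|---|---|---|---|---|
| 0 | 0 / 0 | 0.300 | 0.813 | 0.813 | 0.813 |
| 2% | 0.25 / 0.49 | 0.296 | 0.803 | 0.784 | 0.824 |
| 5% | 0.62 / 1.23 | 0.289 | 0.791 | 0.745 | 0.826 |
| 10% | 1.23 / 2.46 | 0.278 | 0.768 | 0.697 | 0.817 |
| 20% | 2.46 / 4.92 | 0.255 | 0.707 | 0.620 | 0.782 |

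With no effect (0.70 v 0.70) the mean shift is zero and the rejection rate with nearest rounding stays at about 0.03 or below.

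**5. Single-subject examples, 41 per arm.**
- True 28 v 19: p = 0.037. One FLU-v non-case flagged: r = 28/41 = 0.683, count 19.68. Rounded down, p = 0.037; rounded up or to nearest (28 v 20), p = 0.058.
- True 28 v 19, one flagged in each arm: r = 28/40 = 0.70, giving 28.70 v 19.70. The difference is unchanged at 9/41 = 0.220.
- True 28 v 20: p = 0.058. One placebo non-case flagged: 28.70 v 20, rounded to 29 v 20, p = 0.035. Here the error favours FLU-v.

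**6. Complete-case sensitivity analysis.** At q = 10% it gives a mean difference of 0.296 and power of 0.80, close to the truth on average. It does not restore the subject: in the third example it compares 28/40 with 20/41, p = 0.043, against a true 0.058.

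**The case against.** The strongest reply is that few subjects will be affected. They are confined inpatients, swabbed twice daily and assessed daily by a physician, so a two-day swab gap means about four missed swabs in a row. The obvious cause, leaving quarantine early, interrupts both components and usually leaves status open, so missing is then correct. This stands. No document supports 10 or 20%, and at 2 to 5% power is 0.80 to 0.79, essentially the planned figure.

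Next, the planned complete-case analysis nearly recovers the true difference on average, so a reader would see a gross distortion. That also stands, but it is a sensitivity analysis and does not count these subjects as non-cases either.

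Third, imputing the placebo rate in the vaccine arms is a deliberate conservative choice. For subjects whose status is open, it is. It does not justify imputing where the outcome is already known.

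A reader might go further and infer that the rule always biases against FLU-v. It does not: the sign depends on mp − mv. Nor does the SAP say that fractional counts enter Fisher's test. It is silent on conversion, so this is an under-specified step, not proof that the test cannot be run. The secondary rules are partly ambiguous too. A shedder with one symptom and a symptom gap is not expressly assigned under Modified MMID, and SAP 5.7.4 does provide missing-data analyses for continuous endpoints.

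**Conclusion.** The rule gives a wrong value for a definable set of subjects, and the input to the primary test is not fully defined. Under the stated assumptions (2 to 10% of non-cases flagged, the same share in each arm, design rates, nearest rounding), the cost is 1 to 5 points of power and 0.4 to 2.2 points of the rate difference. There is no sign of false-positive inflation with nearest rounding. The practical risk is a borderline result: one flagged subject and an unstated convention can move p across 0.05, in either direction. If no subject is flagged, nothing changes.

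Severity: should-fix. The error is clear and cheap to remove, but its likely size is modest. The secondary-endpoint rules are lower priority; they are worth aligning because the same subject can be missing on the shedding overview and score zero on shedding duration.

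**What to change.** **SAP 5.2.** Code MMID = 0 when either component is negative on all recorded data and has no two-day gap. This keeps the SAP's existing tolerance for isolated missed swabs or assessments. Keep observed cases as cases. Code MMID missing only when neither applies.

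**SAP 5.7.1.** Keep the placebo-rate imputation and the one-sided Fisher's exact test. Define the rate as the placebo proportion among subjects with known MMID, and state a conversion to integers fixed before unblinding. One option is to round the imputed events against FLU-v: up in the FLU-v arm, down in placebo. That moves each count by less than one event and is deliberately conservative. After the change to 5.2 it touches only subjects whose status is truly open, so the power losses in the table would be an overstatement of its cost.

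**SAP 5.4, lower priority.** Set Modified MMID to missing when a shedder has a two-day symptom gap and fewer than two recorded symptoms. Apply the two-day missing rule before assigning a duration of zero, in line with the overview of symptoms and shedding.

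**Cost.** A few lines of SAP text and derivation code. No new data, no change of test and no change of sample size.
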